Experimental design: This proposal seeks to elucidate the differences in reward/appeal, harshness/irritation, nicotine delivery, preference and impact of menthol flavor (compared to control tobacco flavor) between nicotine salt vs free base nicotine e-liquids. Thirty adult menthol smokers (15 male; 15 female) will participate in a double-blind, randomized, cross-over study across three experimental sessions. For the first two sessions, each participant will be randomly assigned to receive nicotine salt or freebase nicotine (both in a concentration of 36mg/ml) on two separate days (see Table 1). Freebase nicotine e-liquid at concentration of 36mg/ml has been used previously in

smokers with no reported adverse effects^{53,54} and this concentration is within range of nicotine concentrations used in nicotine salt e-liquids/e-cigarette pod devices^{55,56}. Following overnight abstinence from combustible tobacco products (CO≤10 ppm), participants will be exposed to the assigned form of nicotine in combination with two flavor conditions (tobacco and menthol) in a counterbalanced randomized order. Each exposure will consist of 2 2-sec puffs and will be separated by a 60-minute washout period (see Table 2).

iSaliva nicotine/ cotinine is an exploratory outcome and nicotine/cotinine levels will be assessed using saliva samples obtained 10 times per session (5 min prior to and 5, 15, 30, 45, and 55 minutes after the onset of puff1, and 5, 15, 30, and 45 minutes after the onset of puff2). Assessing the nicotine/cotinine levels will determine if there are pharmacokinetic differences between nicotine salts vs freebase nicotine. After completing the first two e-cigarette exposure sessions, the same thirty adult menthol smokers (15 female, 15 male) will undergo overnight abstinence from combustible tobacco and nicotine products and participant in a 60-minute choice e-cigarette self-administration session.

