During the third session, each participant will then be exposed to the same e-liquids they were exposed to during the two experimental sessions. During the third session participants can freely self-administer any of the four e-liquids in an e-cigarette pod device (see Table 3). Participants will be left alone in the room to use all four of the e-cigarettes in any order or frequency they choose (Table 1). The third session will be video recorded. This session will be double blinded but to ensure participants distinguish each e-cigarette from each other, the e-cigarettes will be labeled with letters A, B, C, D randomly by a research assistant who is not conducting the study or coding the videos. This labeling will also be helpful for the video coders so they can distinguish e-cigarettes. E-liquids will be measured before and after the session. Two research assistants will independently code the video-tapes for puffing behaviors. Heart rate and blood pressure will be monitored throughout the session for safety, and participants will be told that they can stop anytime if they feel uncomfortable. Per the current practice of [name] research group, participants will be trained on how to puff the e-cigarettes, prior to the self-administration session. Training will be conducted using e-cigarettes that contain the base liquid of 50% propylene glycol(PG)/50% vegetable glycerin(VG).

The third session will be videotaped to ensure experimenter reliability, and to review individual participant's vaping. The commercially available Suorin iShare™ and commercially available e-liquids will be used for our studies. The Suorin iShare™ is a refillable pod system e-cigarette device composed of a battery without voltage control and a refillable pod that contains the e-liquid, mouthpiece and coil. It is among one of the pod e-cigarette devices that are used widely^{57,58}. Participants will not be allowed to keep the device. One month after the third session, participants will receive a follow up phone call to assess any health symptoms via a health assessment list, fatigue and shortness of breath.

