1. General Labeled Magnitude Scale (gLMS)(experimental sessions)¹: For TCORS Menthol pilot, gLMS ratings will be obtained 5, 15, 30, 45, and 55 minutes after each puff during lab 1 and lab 2. Participants will rate coolness, irritation/harshness, cigarette and e-cigarette craving using the gLMS which is a category ratio scale with 7 semantic labels: "no sensation", "barely detectable", "weak", "moderate", "strong", "very strong", and "strongest imaginable". The labels are positioned quasi-logarithmically according to their empirically determined semantic magnitudes. The gLMS will be displayed on a monitor via a custom LabView® program, and participants will make their ratings using a mouse. Ratings are numerically transformed and then used for statistical analyses. For the K01 metabolism study will be assess irritation/harshness, coolness, cigarette craving, e-

cig craving at baseline, 5 and 15 min after nicotine exposure during the directed puffing section of lab sessions.

2. Labeled Hedonic Scale (LHS)(experimental sessions)³ : For TCORS Menthol pilot, liking of e-cigarette taste will be assessed 5 min after each flavor exposure using the LHS scale. The LHS is a bipolar scale with "neutral" in the middle and 5 symmetrical semantic labels: "like/dislike slightly", "like/dislike moderately", "like/dislike very much", "like/dislike extremely", "most liked/disliked imaginable", positioned on the scale according to their semantic magnitude. The LHS yields ratio-level data on the magnitude of liking/disliking of sensation equivalent to that produced by magnitude estimation (ME). This scale will also be displayed on a computer screen as above and numerically transformed.

For K01 metabolism study, liking of e-cig taste will be assessed at baseline, 5 min and 15 min after nicotine exposure during the directed puffing section of lab sessions.

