30 healthy participants will ≥ 21 years of age; smoking menthol cigarettes/cigars/little cigars at least 5 per day, with CO levels ≥ 10 ppm and have ≥ 3 on the urine NicAlert test, willing to abstain from all combustible tobacco products 12 hrs prior to each experimental session, not currently planning to stop smoking, limited experience with e-cigs (not more than 25 times lifetime).

K01 metabolism study

Eighty-five healthy African American participants (43 female and 42 males who smoke) who are ≥ 21 years of age; able to read and write English, smoking at least 5 menthol cigarettes per day on at least 25 days or more in past month^{69,70}, CO ≥ 10 ppm and provide a semi-quantitative urine cotinine result of at least 200 ng/ml assessed with Alere iScreen OFD Cotinine, willing to abstain from tobacco and nicotine products 12 hrs. prior to each lab session, used e-cigarettes at least 10 times in the past six months, do not plan to quit e-cigarette use, not planning a smoking quit attempt ,have not stopped e-cigarette use due to COVID, willing to try e-cigarettes for the study, must report ever JUUL use and/or other nicotine salt/pod e-cigarette devices (i.e., JUUL-like), report regular menthol cigarette use

7. **Subject classification:** Check off all classifications of subjects that will be specifically recruited for enrollment in the research project. Will subjects who may require additional safeguards or other considerations be enrolled in the study? If so, identify the population of subjects requiring special safeguards and provide a justification for their involvement.

Children

Healthy

Fetal material, placenta, or dead fetus

 Non-English Speaking	 Prisoners	 Economically disadvantaged persons
 Decisionally Impaired	 Employees	 Pregnant women and/or fetuses
 Yale Students	 Females of childbearing potential	

NOTE: Is this research proposal designed to enroll children who are wards of the state as potential subjects?

Yes No

8. **Inclusion/Exclusion Criteria:** What are the criteria used to determine subject inclusion or exclusion?

CORE INCLUSION/EXCLUSION CRITERIA FOR BOTH STUDIES:

Inclusion:

- At least 21 years of age
- Able to read and write English.
- Smoking at least 5 menthol cigarettes/cigars/little cigars per day

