The mixed models will include gender (female, male) as a between-subject factor, flavor (menthol, tobacco), nicotine form (salt and freebase) as within-subject factors, and measurement time (time-within-experimental session). The models will also include all possible interactions among nicotine form and flavor and adjust for the stratification variables (sex). We anticipate significant main effects of flavor on liking/wanting of drug effects and e-cigarette taste. In addition, we expect significant main effects of nicotine form on irritation/harshness. Similar models will be used for secondary outcomes (nicotine-induced stimulation, craving and withdrawal).

Statistical Analysis for K01 Metabolism Study: Preliminary analyses will provide an overview of the data (e.g., randomization success, outcome distribution, missingness patterns). Outcome analyses will be intent-to-treat and using mixed-effects models. These models allow for different numbers of observations per subject, use all available data, and can handle missing-at-random data. If model assumptions appear to be violated, we will transform the data or fit more flexible generalized linear or nonparametric mixed models. Aim 1 and Aim 2: The mixed models will include baseline NMR (continuous), time within lab (within-subject factor), flavor (menthol, tobacco; within-subject factor), their three-way interaction, all corresponding two-way interactions and main effects. The model will also adjust for the between-subject factor sex (female, male). We will use Bayesian information criterion (BIC) to select the best fitting correlation structure for the repeated measures within subject. We will use graphical methods and polynomial terms to investigate whether the relationship between NMR and outcomes is linear. Statistical training and support will be provided by my co-mentor [name] who served as the Lead Biostatistician for Yale TCORS 1.0 and currently for Yale TCORS 2.0. She has also led statistical analysis efforts on similar experimental e-cig projects through the Yale TCORS⁶¹. **Power Analysis:** With 85

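### The only puff training described for the TCORS pilot comes before the free self-administration session, not before the two directed sessions that supply the primary ratings; the likely cost is precision

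*Combined protocol and SAP*

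**What the plan says.** Section I.4 (Research Plan, TCORS menthol pilot study) mentions training in its account of the third session: "participants will be trained on how to puff the e-cigarettes, prior to the self-administration session". It adds: "Training will be conducted using e-cigarettes that contain the base liquid of 50% propylene glycol(PG)/50% vegetable glycerin(VG". The order of sessions is explicit: "After completing the first two e-cigarette exposure sessions, the same thirty adult menthol smokers" go on to the choice session.

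For labs 1 and 2 the same section says: "Each exposure will consist of 2 2-sec puffs and will be separated by a 60-minute washout period". Table 2 lists assessments, CO, saliva and directed puffs for these labs, with no practice step. Section I.9 lists consent, histories and biochemical measures at intake, again with no practice.

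The ratings follow the directed exposures. Under Assessments, "gLMS ratings will be obtained 5, 15, 30, 45, and 55 minutes after each puff during lab 1 and lab 2", and "liking of e-cigarette taste will be assessed 5 min after each flavor exposure using the LHS scale". The DEQ items are timed from each puffing. Table 3 shows only CO and e-liquid weighing around session 3.

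On experience, Section I.6 asks for "limited experience with e-cigs (not more than 25 times lifetime", while the core criteria in Section I.8 require ten or more uses within the previous six months. Section I.4 also says that staff give instructions from another location by two-way audio.

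**The concern.** In labs 1 and 2 the way a participant puffs largely determines how much is inhaled, and the exposure is short. In session 3 puffing is free, and by then each completer has already had four directed exposures on the Suorin iShare. The described practice is therefore attached to the session that least needs a standard puff.

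If technique improves with use, ratings and saliva nicotine will shift between the first and later exposures for reasons unrelated to the liquid. Nicotine form differs within a person only between labs, so a lab 1 to lab 2 shift falls on the form comparison. That comparison matters to the plan: Section I.13 states that "we expect significant main effects of nicotine form on irritation/harshness". A shift within lab 1 falls on the flavor comparison.

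Poor technique would also be hard to see afterwards. Video coding and e-liquid measurement are described for the self-administration session, not for labs 1 and 2.

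**Working it through.** The TCORS part gives no alpha, power, effect size or SD, so there is no planned figure to reproduce. From the documents: 30 completers (Section III.1); form randomised to two days and both flavors given each day in counterbalanced order (Section I.4); a model with gender, flavor, form and time within session, and no session, period or sequence term named (Section I.13). The size of any learning shift is an assumption throughout.

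**1. Shift δ common to both exposures of lab 2, orders balanced 15:15.**
- Form contrast (salt minus freebase): each participant's difference moves by +δ or −δ according to order. The mean movement is (15 − 15)/30 × δ = 0.
- Flavor contrast and form-by-flavor interaction: both flavors in a lab carry the same δ, so it cancels. A simulation with shifts of 0.5 and 1.0 residual SD gave a form bias of about 0.00 and an interaction bias of about 0.00.

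**2. Precision of the form contrast with no session term.** The ±δ stays in the residual. With δ in SDs of the within-person form difference, the standard error is multiplied by √(1 + δ²):
- δ = 0.3: √1.09 = 1.044, or +4%
- δ = 0.5: √1.25 = 1.118, or +12%
- δ = 0.8: √1.64 = 1.281, or +28%

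On the power scale (paired t test, n = 30, two-sided 0.05), 80% power needs a standardised difference of 0.53. Dividing 0.53 by √(1 + δ²) lowers power to 78%, 71% and 51% for δ = 0.25, 0.5 and 1.0. Fitting a period term restores about 80%.

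**3. Unequal orders, no session term.** Bias in the form contrast = δ × (n₁ − n₂)/30:
- 17:13 gives 4/30 = 0.13δ
- 18:12 gives 6/30 = 0.20δ
- 20:10 gives 10/30 = 0.33δ

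The documents do not say whether form order is blocked. Under simple randomisation a split of 18:12 or worse has probability 0.36.

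**4. Shift λ confined to the first exposure of lab 1.** This touches one of the four cells. The interaction is (salt-menthol − salt-tobacco) − (freebase-menthol − freebase-tobacco). It moves by +λ if the first exposure was salt-menthol or freebase-tobacco, and by −λ otherwise. Over balanced orders the mean is 0, but λ² is added to the variance. With λ in SDs of that contrast, the multiplier is again √(1 + λ²). A lab-level session term does not remove this part.

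**The case against.** The case against has four parts.

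- **Silence is not exclusion.** The training sentence sets no earliest time and does not say that no training is given before lab 1. A reader might infer that the plan forbids earlier training and sends untrained users into labs 1 and 2. The text does not support that. It supports only the statement that no earlier study training is described.
- **Participants have experience.** Sections I.6 and I.8 together admit people with at least 10 recent and at most 25 lifetime uses, and puffs in labs 1 and 2 are directed by audio. Putting training where participants are left alone has some logic. This lowers the likely size of a learning effect, but neither the criteria nor the audio link provides practice with this device or a timed 2-second puff.
- **The design protects the primary hypotheses.** Both concern menthol's effect across nicotine forms, and a common between-lab shift cancels from that interaction. This stands. A reader might infer that learning confounds the primary comparison; randomised form order and counterbalanced flavor order do not support that.
- **The precision loss is partly a modelling gap.** It arises because no session term is named, and any period effect would produce it. This also stands for the common shift, but not for a shift confined to the first exposure.

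**Conclusion.** The point holds as a low-cost improvement to exposure control; it does not show that the comparison is invalid. As written, practice with the study device and puff pattern would first occur during rated exposures.

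The main consequence is added variance in the salt-versus-freebase contrast: about 4% to 28% on its standard error for assumed shifts of 0.3 to 0.8 SD, if no session term is fitted. Bias in that contrast needs unequal orders. The interaction is unbiased under a common lab shift and loses precision only if learning is concentrated in the first exposure.

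Confidence is high on where training is described. It is moderate on impact, because the documents give no information on whether learning occurs or how large it is. Precision matters here because Section I.13 presents the pilot as a source of effect estimates for a larger study.

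**What to change.** In Section I.4, state that the existing PG/VG training, including practice of the timed 2-second puff, is given at the in-person intake after eligibility is confirmed and before lab 1. If earlier training is already intended, the same sentence should say so.

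Training should not be placed on the day of lab 1's baseline ratings. Section II.B (Background Information) says PG is believed to cause a throat sensation, so same-day practice before lab 1 alone would make the two labs differ on irritation, a primary outcome.

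Naming a session term in the Section I.13 model would absorb a common lab shift from any source. It complements the practice and does not replace it.

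The liquid and staff are those already planned. Costs: some participants who later drop out will have been trained, and the in-person intake, described as very brief, becomes longer. The storage text in Section II.B keeps e-juice and pods inside Pierce lab, while Section I.9 names another site for in-person consent and assessments, so a line on where training pods may be used may be needed.

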Secondary Aim: Examine the influence of menthol flavor on the effects of nicotine (freebase vs salt) stimulation, craving reduction, and alleviation of nicotine withdrawal. Participants will rate nicotine withdrawal and stimulation using the Revised DEQ and cigarette craving using the gLMS.

Exploratory Aim: Examine nicotine delivery following exposure to nicotine salt vs freebase nicotine exposure in combination with flavors (tobacco or menthol) by measuring saliva nicotine levels 5 min prior and 5, 15, 30, 45, and 55 minutes after nicotine and flavor exposure via e-cigarettes

K01 metabolism study

Eighty-Five African Americans (43 F, 42 M) who smoke and have experience with e-cigarettes will participate in a double-blind, randomized, cross-over study across two experimental sessions. Following overnight abstinence from combustible tobacco products (CO≤10 ppm), participants will be randomly assigned to receive an e-cigarette with menthol flavor or control tobacco flavor (both in a concentration of 5% nicotine) on two separate days. Each session will consist of 1 puffing bout (10 puffs, 3 sec each puff, 30 sec puff interval) followed by 2 hours of abstinence, then 60 minutes of ad libitum e-cigarette use. The specific aims are:

Aim 1: Investigate the relationship of menthol flavor (vs tobacco flavor) and nicotine metabolite ratio (NMR) on nicotine pharmacokinetics and subjective effects during directed e-cigarette administration in African Americans who smoke. We hypothesize that during the menthol exposure session participants will have higher plasma nicotine levels compared to the tobacco flavor exposure session. We hypothesize that NMR is negatively associated with nicotine plasma levels during the tobacco flavor exposure sessions. Lastly, we hypothesize that participants will have a larger reduction of cigarette craving in the menthol compared to tobacco session. Primary outcomes: plasma nicotine boost, nicotine area under the curve. Secondary outcome: cigarette craving. Exploratory outcomes: other subjective effects such as liking of e-cig taste. Gender differences will be explored for all outcomes.

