Experimental Design: Aim 1 focuses on the directed e-cigarette administration procedure. Saliva NMR will be assessed at intake appointment and will be a continuous measure in this study^{59,60}. Following overnight abstinence from combustible tobacco products (CO≤10 ppm), African Americans who smoke will participate in a double-blind, counterbalanced and randomized e-cigarette exposure laboratory study where they will receive two e-liquid flavors (menthol, tobacco) with a fixed nicotine salt concentration in e-cigarettes (5%) on two separate days (one flavor condition per session). The directed e-cigarette administration procedure will consist of 1 fixed-puffing bout (puffing bout=10 puffs, 3 sec each puff, 30 sec puff interval) as done previously by my mentor, [name]. Per the procedures conducted by my co-mentor [name] research group^{62,63}, plasma nicotine levels will be assessed at baseline and 5, 15, 30, 45 and 60 minutes after nicotine exposure via e-liquids during the directed e-cigarette administration procedure. Heart rate and blood pressure will be measured at 5, 15 and 30 minutes after the final puff. Participants will rate irritation/harshness, coolness, cigarette craving, e-cigarette craving, liking of e-cig taste, reward/appeal of e-cig, nicotine withdrawal and stimulation at baseline, 5 and 15 min after nicotine concentration exposure. Participants will be told that they can stop anytime if they feel uncomfortable. **Independent variables:** sex (male or female), nicotine metabolite ratio, flavor (menthol, tobacco), **Dependent variables:** primary outcomes- plasma nicotine boost, nicotine area under the curve; secondary outcomes- cigarette craving; exploratory outcomes- reward/appeal of e-cigs, e-cig craving, irritation/harshness, coolness, nicotine withdrawal, stimulation, liking of e-cig taste. We will explore gender differences for all outcomes.

Aim 2: Elucidate the relationship between menthol flavor (vs tobacco flavor) and NMR on nicotine pharmacokinetics and subjective effects during e-cigarette ad libitum use

Eligibility/ Recruitment/Screening: African Americans who participate in Aim 1 will participate in Aim 2.

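### K01 cigarette craving is rated before each bout, but the plan neither adjusts for that rating nor names the contrast that tests the craving hypothesis

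*Combined protocol and SAP*

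**What the plan says.** All references are to the combined protocol and SAP.

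- **Status and hypothesis.** For K01 Aim 1, section I.4 has "secondary outcomes- cigarette craving". Section I.1 expects that "participants will have a larger reduction of cigarette craving in the menthol compared to tobacco session". That is a statement about change from the pre-bout state.
- **Schedule.** Section I.4 (K01 Aim 1, Experimental Design) puts cigarette craving in the list that ends "nicotine withdrawal and stimulation at baseline, 5 and 15 min after nicotine concentration exposure". Assessments item 1 repeats this for the gLMS scales: "cig craving at baseline, 5 and 15 min after nicotine exposure during the directed puffing section of lab sessions". Each participant therefore gives three craving ratings around the directed bout in each of two sessions, and the first precedes any study flavor that day.
- **Model.** Section I.13 gives one paragraph for Aims 1 and 2: "The mixed models will include baseline NMR (continuous), time within lab (within-subject factor), flavor (menthol, tobacco; within-subject factor), their three-way interaction", with "all corresponding two-way interactions and main effects". It also adjusts for sex. The only baseline quantity in the model is NMR.
- **Not stated.** The paragraph does not list the levels of time within lab. It does not say whether the pre-bout craving rating is a response or a covariate, and it does not say which term tests the craving hypothesis.

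**The concern.** Flavor cannot affect a rating made before the bout. If that rating is one of three response times, a flavor effect averaged equally over time mixes one time with no possible effect and two times that can show one. The flavor-by-time term avoids this dilution. As a default test, however, it spends two degrees of freedom on what is essentially one question, and it uses the baseline only by subtraction, which carries the baseline's full noise into the comparison.

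With no contrast named, the reported flavor effect on craving could be any of several quantities with different meaning and power, and one of them depends on how the software codes the factors. At stake is efficiency and clarity for a secondary outcome. The ratings needed to do better are already scheduled.

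**Working it through.** **The plan's own figures.** Section I.13 states 80% power with 85 participants, two-sided alpha 0.05, for a correlation of 0.30 and for a within-subject d of 0.32, both for the primary outcomes. The correlation figure reproduces (80.0% by Fisher z). A paired t-test with d=0.32 gives 83.1%; the d detectable with 80% power is 0.307. The stated 0.32 is slightly conservative and does not bear on this point.

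**Setup.** Let D0, D5 and D15 be the menthol-minus-tobacco differences in craving within a participant at baseline, 5 and 15 minutes.

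- From the documents: n=85, alpha 0.05 two-sided, and the three rating times.
- Assumed: mean differences 0, δ, δ; SD 1 at each time; a common correlation ρ between any two of the differences, shown at 0.3, 0.5 and 0.7; and δ=0.32. The plan gives neither ρ nor a craving effect size; 0.32 is borrowed from the primary outcomes.

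**What each contrast estimates.**

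- Equally weighted flavor main effect over three times: (0 + δ + δ)/3 = 0.667δ.
- Mean of 5 and 15 minutes minus baseline: δ.
- Mean of 5 and 15 minutes, adjusted for D0: δ.

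A simulated fit with a true post-bout effect of -1.00 agrees. With sum-to-zero coding the flavor term was -0.69. With baseline as the reference level the flavor coefficient was -0.01, the pre-bout difference alone, and the two flavor-by-time terms were -1.02 and -1.01.

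**Variance of each contrast.**

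- Main effect: (1+2ρ)/3
- Post-bout mean alone: (1+ρ)/2
- Change: (1+ρ)/2 + 1 - 2ρ
- Baseline-adjusted: (1+ρ)/2 - ρ²

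For the 1-df tests, power comes from a noncentral t with 84 df and noncentrality √85 × (estimated effect)/√variance. For the 2-df flavor-by-time test, the noncentrality is 85 × 0.32² × 2/(3(1-ρ)), which is 8.29, 11.61 and 19.34, referred to F with 2 and 83 df. The 1-df change contrast has the same squared noncentrality (for example 85 × 0.32²/1.05 = 8.29), so the omnibus loses power only through its extra degree of freedom.

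| Test | ρ=0.3 | ρ=0.5 | ρ=0.7 |
|---|---|---|---|
| Flavor main effect, three times | 76% | 66% | 58.5% |
| Flavor-by-time, 2 df | 72% | 86% | 98% |
| Change from baseline, 1 df | 81% | 92% | 99% |
| Post-bout mean, baseline ignored | 95% | 92% | 89% |
| Post-bout mean, baseline-adjusted | 97% | 98% | >99% |

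**Efficiency of adjustment over change** (variance ratio, equivalent to a sample-size ratio): 1.05/0.56 = 1.88; 0.75/0.50 = 1.50; 0.45/0.36 = 1.25.

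**Sensitivity to scaling.** If d=0.32 is set for the mean of the two post-bout ratings instead of for each rating, power at ρ = 0, 0.2, 0.5 and 0.8 is:

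- main effect: 66, 60, 54 and 51%
- change contrast: 39, 54, 83 and >99%
- baseline-adjusted: 83, 86, 95 and >99%

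The levels move, but adjustment remains the best of these three throughout.

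**The case against.** A reader might infer that the plan puts the baseline on the wrong side of the model, so that a third of the tested menthol effect is measured before any flavor is given. The documents do not support that, for four reasons.

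- Section I.13 never says that baseline is a level of time. The same paragraph serves every outcome, including nicotine boost and area under the curve, which are summaries with no such levels. It cannot be read as fixing the levels for craving.
- It never names the averaged flavor effect as the craving test. Flavor-by-time is in the model and matches the hypothesis of a larger reduction without dilution.
- The 2/3 figure needs equal weights over three times. Under reference coding the flavor coefficient means something else.
- Keeping baseline as a response is legitimate. The change contrast is valid, and a model that constrains the baseline means to be equal across flavors is about as efficient as covariate adjustment.

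The size of the gain also rests on assumed correlations and an assumed effect size. At ρ=0.7 adjustment adds under one point to the 1-df change contrast and about two points to the omnibus test. Craving is secondary, and the power statement covers primary outcomes only.

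All of this stands, and it rules out calling the plan biased or wrong. What it leaves is that a baseline is collected in every session, has no stated role, and could be used to better effect than by any contrast the listed terms offer.

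**Conclusion.** The point holds as a free improvement on a secondary outcome. The documents establish that craving is rated before each bout, that no session-baseline craving covariate is planned, and that no contrast is named for the hypothesis. The dilution to 2/3 is conditional: it applies only if baseline is a level of time and the test is an equally weighted flavor main effect.

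Against the valid 1-df change contrast, baseline adjustment is worth 1.25 to 1.88 times the sample size over correlations of 0.7 down to 0.3. In power the gain runs from about 16 points at ρ=0.3 to almost nothing at ρ=0.7. These figures assume equal variances, one common correlation, the same effect at 5 and 15 minutes, and d=0.32 at each. They are illustrations, not estimates of this trial's power for craving. No bias is shown, and no primary outcome is shown to be affected.

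**What to change.** Add a short paragraph to section I.13 for craving and the other K01 scales whose pre-bout rating is meaningful, and list those scales:

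1. Model the 5- and 15-minute ratings as the responses. Include that session's baseline rating and the participant's mean baseline over the two sessions as covariates, so that within- and between-participant baseline differences are separated. About equally efficient: keep baseline as a response and constrain its mean to be equal across flavors.
2. Name one test of the craving hypothesis: the 1-df menthol-minus-tobacco contrast averaged over 5 and 15 minutes. Because flavor interacts with NMR in the model, state that it is evaluated at the sample mean NMR.
3. Report flavor-by-time over the two post-bout ratings as supportive only.

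The cost is SAP wording, settled before the data are unblinded. It needs no new ratings, visits or participants.
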